### **Statistical processing of results**

Statistical processing of the data obtained was performed using Statistica version 12 (StatSoft, USA). Values are presented as Me (25 - 75), where Me is the median and 25 and 75 are the interquartile ranges as 25th and 75th percentiles. The normality of the distribution of values was assessed using the Shapiro-Wilk W criterion. Given the lack of normal distribution in the samples studied, non-parametric methods were used to compare groups of data and study correlations. The Mann-Whitney U-criterion was used to compare two independent samples. A significance level of  $p < 0.05$  was used as the criterion for reliability of differences between indicators.

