**Principal Investigator:**

**[name]**

**Sponsor:**

**The Republican Research and Practical Center for Epidemiology and Microbiology**

**Document Date:**

**June 06, 2024**

## **Collection of peripheral blood for the study**

We collected 5-10 ml of venous blood under aseptic conditions into two tubes. One tube with anticoagulant (heparin solution or ethylenediaminetetraacetate (EDTA)), the second tube with blood coagulation activator. The closed vacutainer with blood is inverted several times to mix the blood with the anticoagulant. The patient's blood was delivered to the Immunology and Cell Biotechnology Laboratory within no more than 4 hours of collection.

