## **Sample Preparation for the Study of Spontaneous and Stimulated Production of Oxygen Radicals (ROS) by Blood Neutrophils**

Sample preparation involves the following steps:

- Labelling (positive '+' - stimulated sample and negative '-' - unstimulated sample) and serial numbering of sample tubes;
- Place the cytometer tubes in a rack and number them;
- Add 1 µl of DHR to the tubes;
- Add 50 µl of RPMI medium;
- Add 50 µl of blood and mix thoroughly;
- Incubate for 10 minutes at +37°C;
- Add 20 µl RPMI to '+' samples only and mix the contents of the tube;
- Incubate for 30 min at +37°C in the thermostat;
- Add 2 ml lysis solution, mix tube contents;
- Incubate for 10 min at +16 - +30°C in the dark;
- Centrifuge the tubes (200-300 g - 5 minutes) to precipitate the leucocytes;
- Add 100 µl DPBS and mix.

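### Does the plan need a paired test, or a named ROS comparison, because each patient gives a spontaneous and a stimulated value?

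*Combined protocol and SAP*

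**What the plan says.** The section on sample preparation for oxygen radicals covers two quantities, spontaneous and stimulated production by blood neutrophils. It prepares two kinds of tube, "positive '+' - stimulated sample and negative '-' - unstimulated sample". Both go through the same steps except one addition, made as "RPMI to '+' samples only and mix the contents of the tube".

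The blood collection section describes "One tube with anticoagulant (heparin solution or ethylenediaminetetraacetate (EDTA)), the second tube with blood coagulation activator". Only the first of these holds unclotted blood, so the natural reading is that both ROS aliquots come from the same patient's anticoagulated sample. The document does not say so in words.

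The section on statistical processing of results is the whole analysis plan. It says "non-parametric methods were used to compare groups of data and study correlations", then "The Mann-Whitney U-criterion was used to compare two independent samples", and closes with a 0.05 significance level that "was used as the criterion for reliability of differences between indicators". It does not list the ROS comparisons, define a stimulated-minus-spontaneous difference or a ratio, or name a paired test.

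**The concern.** Two things look wrong.

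First, a stimulated and an unstimulated reading on the same blood are a textbook pair. If the only named test is for independent samples, an analyst might apply it to the pair. That ignores the within-patient correlation and can lose power.

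Second, the ROS variable is not defined. Spontaneous output, stimulated output, their difference and their ratio answer different questions: baseline activation, total output, and reactivity on two scales. If the quantity reported were the one that happened to reach significance, the nominal 5% would no longer describe the error rate. The closing phrase about differences between indicators could be taken to leave a stimulated-versus-unstimulated test open.

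**Working it through.** The plan states no sample size, standard deviation, correlation or effect size, so there is no figure of its own to reproduce. Only the 0.05 level comes from the document; it is taken as two-sided. All other inputs below are assumptions, shown as ranges.

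**1. Is a within-patient test planned?** The general sentence speaks of comparing groups of data, and the test sentence restricts Mann-Whitney to independent samples. The heading on cellular immunity uses the word indicators for measured parameters. A difference between indicators is therefore most simply read as a parameter that differs between groups. No section states a stimulated-versus-unstimulated contrast.

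**2. Is the between-group reading valid?** Each patient contributes one value per parameter to each test, so independence holds within each test whatever the correlation between the two readings. In null simulations (log-normal pairs, 20 or 30 per group, correlation 0 to 0.9, 10,000 datasets per setting) single Mann-Whitney tests rejected in 4.3 to 5.4%.

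**3. What does having two ROS values cost?** If the two tests were independent, the chance of at least one rejection would be 1 − 0.95² = 9.75%. Positive correlation lowers it. The simulated range is 6.6 to 9.9%, with the top end within simulation error of 9.75%. A figure of 11.1 to 14.1% arises for four tests, but that adds a difference and a ratio which appear nowhere in the document.

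**4. If Mann-Whitney were used on the pairs, would false positives rise?** No. Bivariate normal pairs, no shift, 20 pairs, 10,000 datasets per setting:

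| Correlation | Mann-Whitney | Signed-rank |
|---|---|---|
| 0 | 5.0% | 4.8% |
| 0.3 | 2.0% | 4.6% |
| 0.5 | 0.9% | 5.0% |
| 0.7 | 0.2% | 5.0% |

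**5. Would power be lost?** That depends on how strong stimulation is. With a shift of 0.5 SD, correlation 0.5 and 20 pairs, power is 28% for Mann-Whitney and 55% for signed-rank. On the log scale the shift in SD units is ln(fold)/SD:

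| Fold rise | log-SD 0.25 | log-SD 0.5 | log-SD 1.0 |
|---|---|---|---|
| 1.5 | 1.62 | 0.81 | 0.41 |
| 3 | 4.39 | 2.20 | 1.10 |
| 10 | 9.21 | 4.61 | 2.30 |

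So 0.5 SD lies near the bottom of this range. With 20 log-normal pairs, correlation 0 to 0.9 and 4,000 datasets per setting, both tests have about 100% power in six of the nine cells (shift 1.62 SD or more). At 1.10 SD they differ by at most about 5 points, and Mann-Whitney is ahead at zero correlation (90.5% against 85.0%). A sizeable loss appears only at 0.81 and 0.41 SD; for example, at correlation 0.5, 73% against 90% and 17% against 35%.

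**The case for a change.** The strongest case for a change is that the gap is real and cheap to close. The linkage between the two readings is a strong inference, the analysis section is complete as supplied, and nothing in it tells a reader which ROS quantity a reported p-value tests. Groups can differ on reactivity and not on baseline output, so the choice affects interpretation. A sentence or two would settle it.

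The factual part stands: the ROS comparisons are not listed and no paired test is named. It does not carry the conclusion, for three reasons.

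- The paired-test point depends on an analysis that the plan does not state. A plan need not name a test for a contrast it does not propose.
- The lack of a named main comparison is not peculiar to ROS. The flow cytometry panel and the annexin/propidium iodide assay have equally unlisted comparisons. Naming a main ROS comparison would leave the rest of the panel as it was.
- The analysis section is written in the past tense. Choosing a main comparison now could not restore a 5% level that selection had already eroded, and recording what was chosen beforehand helps only if such a record exists.

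**Conclusion.** No change to the plan follows. Between-group Mann-Whitney tests of spontaneous and of stimulated ROS hold their level, the restriction to independent samples is correct, and no section applies that test to paired data. What is missing is a list of which ROS values were compared. An analyst would supply this in the ordinary way by reporting both raw comparisons, and by using a signed-rank test if a within-patient contrast were ever made.

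The size is small. On the two documented quantities the chance of at least one false positive is 6.6 to 9.9%. Misuse of Mann-Whitney on the pairs would make it conservative, with a power loss running from none to large as stimulation gets weaker and correlation higher.

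The conclusion rests on reading the comparisons as between groups, which the wording supports but does not spell out, and on assumed sample sizes, correlations and effects. A stated within-patient contrast, or a reported difference or ratio chosen after the results were seen, would reopen the question.
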